5.2.5.3 Censoring after intercurrent events

The primary analysis (Section 5.2.3) will be repeated with the data censored after the intercurrent event of premature discontinuation of the study treatment. The estimate of this analysis reflects the treatment effect of BIIB092 if the drug is taken as directed.

5.2.5.4 Per-protocol analysis

The per-protocol analysis will be done using the same model as the primary analysis (Section 5.1) and applied in the per-protocol population (Section 3.2).

5.2.5.5 Responder analysis

To further assess whether subjects on BIIB092 progress differently from those on placebo, responder analysis will be conducted. The responders will be determined by a threshold of the primary endpoint, i.e., subjects whose change from baseline PSPRS at Week 52 is smaller than or equal to the threshold will be classified as responders (not worsening) and otherwise will be classified as non-responders (worsening). All subjects with missing data at Week 52 will be classified as non-responders.

The responder analysis will be conducted for two threshold values i.e., subjects whose change from baseline in 28-item PSPRS at Week 52 are less than or equal to the threshold values. The number of responders and the response rate will be summarized by treatment group. The dichotomized response, responder vs. non-responder, will be modeled using a logistic regression adjusting for the following variables: treatment group, baseline PSPRS, baseline Color Trails 2 test (≤ 170 or > 170 seconds) and region. In addition to the two selected threshold values, the continuous responder curve that displays the percentage of responders under a wide range of threshold values will be presented by treatment group. The same analyses will be applied to 15-item PSPRS total score using two other threshold values. The threshold values determined using anchor- and distributed-based methods on Davunetide study data are: 6 points and 11 points for 28-item PSPRS change score; 4 points and 9 points for 15-item PSPRS change score.

Since all missing data will be considered as non-response, which is a special form of missing-not-at-random, this analysis can provide additional insights for the robustness of the primary analysis results.

5.2.5.6 Slope analysis

Slope analysis will be conducted to assess the difference between the BIIB092 treatment group and placebo group in the slope of change from baseline in PSPRS up to Week 52. A reduction in the slope of the BIIB092 treatment group compared with placebo group would indicate a slower rate of disease progression, thus reflecting a disease modifying effect of BIIB092. A MMRM model will be used, with dependent variable as the change from baseline score in PSPRS at each visit and with fixed effects of treatment group, time (continuous), treatment group-by-time interaction, baseline PSPRS score, (baseline PSPRS score) by time interaction, baseline Color Trails 2 test (≤ 170 or > 170 seconds) and region. The continuous time variable is calculated as number of years since the 1st infusion, so the slope estimate reflects the annual rate of change. The same methods as in the primary analysis of each endpoint will be considered for the covariance structure and the degrees of freedom.

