5 EFFICACY DATA

5.1 General Considerations

The analysis population for efficacy analysis is the ITT population and data from both the placebo-controlled and OLE periods will be included. All efficacy analyses will be presented by BIIB092 late start and BIIB092 early start groups, and along with the by-visit comparison between the two groups.

There will be no multiple comparison adjustments.

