5.1.1 Visit windows for mapping efficacy endpoint

For efficacy data that are summarized or analyzed by visit, data collected on all scheduled visits and all unscheduled visits will be mapped to an appropriate analysis visit using the windowing scheme shown in Tables 2-6. If there are 2 or more assessments available in the same analysis window for a subject, the assessment that is closest to the target visit day will be used for analysis. If there are 2 or more assessments in the same analysis window with the same distance from the target visit day, the later assessment will be used.

Table 2 Visit Windows for Primary Endpoint: PSPRS

| Analysis visit | Target visit day | Analysis visit window |
|-----------------------|-------------------------|--|
| Baseline | 1 | Most recent non-missing value on or prior to the first dose date |
| Week 12 | 85 | [43, 126] |
| Week 24 | 169 | [127, 210] |
| Week 36 | 253 | [211, 294] |
| Week 48 | 337 | [295, 350] |
| Week 52 | 365 | [351, 378] |

Table 3 Visit Windows for Key Secondary Efficacy Endpoints (MDS-UPDRS, CGI, PSP cognitive composite battery, and PSP-QoL) and RBANS

| Analysis visit | Target visit day | Analysis visit window |
|-----------------------|-------------------------|--|
| Baseline | 1 | Most recent non-missing value on or prior to the first dose date |
| Week 12 | 85 | [43, 126] |
| Week 24 | 169 | [127, 210] |
| Week 36 | 253 | [211, 308] |
| Week 52 | 365 | [309, 378] |

Table 4 Visit Windows for Other Secondary Efficacy Endpoints: SEADL, Phonemic Fluency Test, WAIS-IV Letter Number Sequencing Task, Color Trails test, and MoCA

| Analysis visit | Target visit day | Analysis visit window |
|-----------------------|-------------------------|--|
| Baseline | 1 | Most recent non-missing value on or prior to the first dose date |
| Week 12 | 85 | [43, 126] |
| Week 24 | 169 | [127, 210] |
| Week 36 | 253 | [211, 294] |
| Week 48 | 337 | [295, 434] |

Table 5 Visit Windows for Tertiary/Exploratory endpoints: [REDACTED] and [REDACTED]

| Analysis visit | Target visit day | Analysis visit window |
|----------------|------------------|---|
| Baseline | 1 | Most recent non-missing value on or prior to the first dose date, except for [REDACTED] |
| Week 24 | 169 | [85, 252] |
| Week 48 | 337 | [253, 434] |

Table 6 Visit Windows for volumetric MRI

| Analysis visit | Target visit day | Analysis visit window |
|----------------|------------------|-----------------------|
| Baseline | 1 | <=84 |

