5.2.5.7 Divergence effect analysis

A divergence effect analysis will be performed to assess whether the treatment difference between the BIIB092 treated subjects and the placebo subjects increases over time [Li 2017]. A linear trend test will be conducted on treatment difference at Week 12, 24, 36, 48 and 52 estimated from the MMRM model of Section 5.2.3, to assess if the slope of the treatment difference is positive or not.

Let the estimate of treatment difference be δ_i at time point t_i , where $t_i = 12, 24, 36, 48,$ and 52 (week). The least-square estimate of the slope is

$$\beta_{DIF} = \frac{\sum(t_i - \bar{t})\delta_i}{\sum(t_i - \bar{t})^2},$$

where \bar{t} is the mean of t_i 's. The hypothesis to be tested is

$$H_0: \beta_{DIF} \leq 0 \quad \text{versus} \quad H_a: \beta_{DIF} > 0.$$

Given β_{DIF} is a linear combination of the treatment difference δ_i , this analysis can be implemented by the “estimate” statement in the SAS proc mixed procedure.

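### The slope analysis reads a reduced slope as disease modification, but the slope contrast alone cannot show that, nor any benefit at Week 52

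*SAP*

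**What the plan says.** Section 5.2.5.6 of the placebo-controlled SAP states that a smaller slope on BIIB092 than on placebo would point to slower progression, "thus reflecting a disease modifying effect of BIIB092". It attaches no condition on the Week 52 difference, on the fitted treatment main effect or on linearity.

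The model takes as "dependent variable as the change from baseline score in PSPRS at each visit", with "fixed effects of treatment group, time (continuous), treatment group-by-time interaction" plus baseline terms, the Color Trails 2 category and region. Time is "calculated as number of years since the 1st infusion". Scheduled post-baseline PSPRS ratings are at Weeks 12, 24, 36, 48 and 52; the Week 12 analysis window in section 5.1.1 runs from day 43 to day 126.

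Table 1 in section 5.1 lists the slope analysis as supplementary, and section 5.1.3 makes no multiplicity adjustment for supplementary analyses. Section 5.3.1.5 repeats the slope analysis for the key secondary endpoints.

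**The concern.** With a change-from-baseline outcome the two arms cannot differ at time zero. The model nevertheless estimates a treatment main effect, which is the fitted arm difference at time zero. Once that is free, the treatment-by-time term no longer says how far BIIB092 is ahead of placebo. It says only in which direction the gap is moving across the rated visits. A gap can move in BIIB092's favour while BIIB092 is never ahead.

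There is a second, separate problem. A symptomatic effect that builds up gradually and a true slowing of the disease can give the same widening gap. A 52-week parallel comparison cannot tell them apart.

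What is at stake is one statement in the report. Disease modification is a much stronger claim than a Week 52 difference, and the SAP supplies the wording for it in advance.

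**Working it through.** **The plan's own figure.** Protocol section 17.1 gives 80% power for 3.2 points with SD 9.95, 230 and 115 completers, and two-sided alpha 0.05. The standard error is 9.95 × √(1/230 + 1/115) = 1.136, so 3.2/1.136 = 2.816 and power is Φ(2.816 − 1.96) = 80.4% (80.2% by the noncentral t). The figure reproduces. The documents give no design figure for the slope analysis.

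**Set-up.** Let D(t) be the mean difference in change, BIIB092 minus placebo. Higher PSPRS is worse (placebo-controlled SAP, section 5.2.2), so positive D is harm. The model fits D(t) = a + b·t, with t in years. From Week 12 to Week 52 is 40/52 = 0.769 years. For a difference that is linear across the visits:

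b = (D52 − D12)/(40/52) and a = D12 − b × 12/52

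| Profile (assumed) | D12 | D52 | Slope difference b (points/year) | Main effect a |
|---|---|---|---|---|
| Early deficit that closes | +2 | 0 | −2/0.769 = −2.6 | +2.6 |
| Early deficit that shrinks but remains | +4 | +1 | −3/0.769 = −3.9 | +4.9 |
| Symptomatic benefit that builds from Week 12 | 0 | −3.2 | −3.2/0.769 = −4.16 | +0.96 |
| Proportional slowing from time zero | −0.74 | −3.2 | −3.2 | 0 |
| Constant benefit from Week 12 | −3 | −3 | 0 | −3 |

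Because the first four profiles are straight lines over the visits and the fifth is flat, least squares and generalised least squares give the same answer.

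- The first row gives 2.6/3.2 = 81% of the slope from a true slowing of the design size, with no Week 52 difference.
- In the second row BIIB092 is worse at every visit, yet the slope difference is larger than under true slowing.
- The third row needs no early harm and gives a larger slope difference than true slowing.
- The last row shows the converse: a real, lasting benefit with no slope reduction.

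**Chance of a significant slope reduction in the first row.** The documents give no visit-to-visit covariance, so four structures were assumed, each scaled to SD 9.95 at Week 52: a random slope; compound symmetry with correlation 0.7; autoregressive at 0.85 per 12 weeks with growing SD; and the same with constant SD. With 230 and 115 completers, a two-sided significant reduction occurs in 49% to 76% of trials.

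**Does the divergence analysis protect against this?** Section 5.2.5.7 fits a least-squares line to the "treatment difference at Week 12, 24, 36, 48 and 52 estimated from the MMRM model". That line also has a free intercept. In the first row the differences fall by 2/40 = 0.05 points per week, or 0.05 × 52 = 2.6 points per year, which is the same answer.

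**The case against.** The case for leaving the text alone is mainly about weight, and most of it stands. The clause is one explanatory sentence in a supplementary analysis, with no threshold and no success criterion. Primary inference is the Week 52 MMRM difference, and the key secondary hierarchy does not use the slope. Section 5.2.3 already plans a line plot of adjusted mean change over time and a Week 52 bar plot, so an early deficit that closes would be visible. What does not stand is the inference itself: nothing else in either SAP or the protocol qualifies it.

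Several stronger readings are tempting, and the documents do not support them.

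- A reader might infer that the trial could declare benefit although its primary endpoint shows none. No decision rests on the slope, and the primary result would be reported alongside it.
- A reader might infer that early worsening on BIIB092 is expected. The protocol describes earlier studies as well tolerated and gives no sign of early PSPRS worsening.
- A reader might blame the lack of ratings before Week 12. The gap is only in scheduled post-baseline ratings: there are screening and Week 0 ratings, the Week 12 window opens at day 43, and early-discontinuation ratings may fall sooner. The algebra needs only the free time-zero difference and a difference that does not grow in proportion to time.
- A reader might require that the fitted main effect not favour placebo. Under true proportional slowing its expected value is 0, so the estimate favours placebo half the time. Among significant slope reductions it does so in 54% to 65% of trials under the four assumed covariances, so that rule would discard most true positives.
- A reader might move the disease-modification claim to the extension SAP, whose section 5.1 presents the early-start and late-start groups "along with the by-visit comparison between the two groups". That comparison includes open-label treatment, has no multiplicity adjustment, and states no delayed-start hypothesis or persistence margin. It is not a ready basis for the claim.

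**Conclusion.** The point holds as a correction to the interpretation, and it is minor. A reduced slope under this model does not establish disease modification and does not by itself establish any Week 52 benefit. The slope differences of −2.6 and −4.16 points per year are exact for the assumed straight-line profiles. The 49% to 76% rests on assumed covariances as well as on the assumed 2-point deficit. Neither says how likely such profiles are. The primary estimate, the testing hierarchy and type I error control are unaffected.

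**What to change.** In section 5.2.5.6, delete "thus reflecting a disease modifying effect of BIIB092". State instead that a reduced slope is consistent with slower clinical decline only when the primary Week 52 MMRM difference for the endpoint concerned is statistically significant in favour of BIIB092. Show the slope beside the by-visit differences and the fitted treatment main effect with its confidence interval. The main effect should be descriptive only, not a condition. Do not name the extension-period early-start versus late-start comparison as the basis for a disease-modification claim.

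The Week 52 condition guards against the closing-deficit pattern. It cannot separate symptomatic benefit from disease modification, which is why the clause has to go rather than be qualified.

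The change is about two sentences plus one reported estimate, and the model stays as it is. The cost is a weaker claim from a supplementary analysis. Under true proportional slowing to 3.2 points, the slope would be significant but Week 52 would not in about 16% of trials under compound symmetry, and in 6% and 8% under the growing-SD and constant-SD autoregressive structures. In those trials the favourable wording would be withheld.

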5.2.5.7 Divergence effect analysis

A divergence effect analysis will be performed to assess whether the treatment difference between the BIIB092 treated subjects and the placebo subjects increases over time [Li 2017]. A linear trend test will be conducted on treatment difference at Week 12, 24, 36, 48 and 52 estimated from the MMRM model of Section 5.2.3, to assess if the slope of the treatment difference is positive or not.

Let the estimate of treatment difference be δ_i at time point t_i , where $t_i = 12, 24, 36, 48,$ and 52 (week). The least-square estimate of the slope is

$$\beta_{DIF} = \frac{\sum(t_i - \bar{t})\delta_i}{\sum(t_i - \bar{t})^2},$$

where \bar{t} is the mean of t_i 's. The hypothesis to be tested is

$$H_0: \beta_{DIF} \leq 0 \quad \text{versus} \quad H_a: \beta_{DIF} > 0.$$

Given β_{DIF} is a linear combination of the treatment difference δ_i , this analysis can be implemented by the “estimate” statement in the SAS proc mixed procedure.

5.3 Secondary Efficacy Endpoints

5.3.1 Key Secondary Efficacy Endpoints

The key secondary endpoints include MDS-UPDRS Part II, CGI-C, PSP cognitive composite battery and PSP-QoL. The sequential test described in Section 5.1 will be used to test the key secondary endpoints in the following order: MDS-UPDRS Part II, CGI-C, PSP cognitive composite battery, PSP-QoL physical scale, PSP-QoL mental scale and PSP-QoL VAS. An overall summary of all key secondary endpoints will be provided. A line plot of adjusted mean change from baseline over time and a bar plot of adjusted mean change from baseline at Week 52 will be provided for all key secondary endpoints with the exception for CGI-C where only adjusted mean will be used. Listings will be provided for all secondary efficacy endpoints.

5.3.1.1 Primary analysis of MDS-UPDRS Part II

The MDS-UPDRS Part II includes 13 items assessing motor aspects of experiences of daily living. These include speech, saliva and drooling, chewing and swallowing, handwriting, doing hobbies and other activities, eating tasks, tremor, dressing, hygiene, turning in bed, getting out of bed, walking and balance, and freezing. Each individual item has a 5-point scale, ranging from 0 to 4: 0 for “Normal”; 1 for “Slight”; 2 for “Mild”; 3 for “Moderate”; and 4 for “Severe”. The total score is calculated by adding all required item scores, and ranges from 0 to 52.

The primary analysis of change from baseline MDS-UPDRS Part II scores will be based on the base MMRM model described in Section 5.1. A line plot of adjusted mean change from baseline over time and a bar plot of adjusted mean change from baseline at Week 52 will be provided.

5.3.1.2 Primary analysis of CGI-C

The CGI-C form is the second part of a two-part structure CGI interview. It is intended to determine the change in the participant’s current clinical status, relative to the baseline visit, where CGI-S is used. The CGI-S measures the overall clinical global impression of disease severity using a 7-point scale. The CGI-C scale measures the change in the participant’s change in clinical status from the baseline visit at a specific time point using a 7-point scale: 1 for “Marked Improvement”; 2 for “Moderate Improvement”; 3 for “Minimal Improvement”; 4 for “No Change”; 5 for “Minimal Worsening”; 6 for “Moderate Worsening”; 7 for “Marked Worsening”. Only one answer can be chosen.

The CGI-C scores will be summarized by treatment group at each post-baseline visit. An MMRM model will be used as the primary analysis to analyze CGI-C using fixed effects of treatment group, time (categorical), treatment group-by-time interaction, baseline CGI-S, baseline CGI-S by time

interaction, baseline Color Trails 2 test (≤ 170 or > 170 seconds) and region. The same methods as in the primary analysis will be considered for the covariance structure and the degrees of freedom. A line plot of adjusted mean over time will be provided.

5.3.1.3 Primary analysis of PSP cognitive composite battery

The PSP cognitive composite battery will be used to identify and characterize abnormal cognitive decline in PSP subjects. The PSP cognitive composite battery includes 13 sub-tests in total: 11 tests from the RBANS (only the picture naming is excluded), letter number sequencing test, and phonemic fluency test. The factor analysis suggested three domains:

- Memory and learning: List Learning, Story Memory, List Recall, List Recognition and Story Recall
- Visual-Motor function: Figure Copy, Coding and Figure recall
- Working memory and Executive: Semantic Fluency, Digit Span, Line Orientation, Letter Number Sequencing test and Phonemic Fluency test

For each of the 13 sub-tests, a z-score will be calculated based on scores from baseline data of PASSPORT study. [REDACTED]

[REDACTED]

[REDACTED]

[REDACTED]

[REDACTED]

The z-score for each domain is calculated as the sum of z-scores of the completed tests divided by the number of tests completed. A final total composite z-score of the PSP cognitive composite battery is calculated as the average of three domain z-scores. If there are any missing values for domain z-scores, then no final composite z-score will be calculated.

The RBANS is collected at Weeks 0, 12, 24, 36, and 52, while the letter number sequence test and phonemic fluence test are collected at Weeks 0, 12, 24, 36, and 48. The windowing rule of RBANS (Section 5.1.1 Table 3) will be applied to all sub-tests.

The composite z-score will be used for the primary analysis of the PSP cognitive composite battery using the base MMRM model described in Section 5.1. A line plot of adjusted mean change from baseline over time will also be provided.

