5.1.2 Handling of missing items for scales

If any of the individual items for the MDS-UPDRS Part II and MoCA is missing, the total score of the corresponding endpoint will be imputed by prorating the observed scores [van Ginkel 2010].

- For MDS-UPDRS Part II, if 3 or fewer of 13 items (<25%) are missing, the total score will be imputed by the prorating algorithm. If more than 3 items are missing, the total score of MDS-UPDRS Part II at that visit will be considered missing.
- For MoCA, if 1 domain (<25%) of the 7 domains is missing, the total score will be imputed using the same prorating algorithm; if more than 1 domains are missing, the total score at that visit will be considered as missing.

For CTT 1 and 2, if any test scores are missing due to participant too impaired, participant refused, refusal (subject or informant), physical reason, or too impaired (cognitively or psychiatrically), the missing values will be imputed to 240 seconds. If subjects failed the CTT pretest (hence no CTT was assessed), or did not complete CTT within the time limit of 240 seconds, the missing values will be imputed to 240 seconds as well.

For Letter number sequence test, if partial item scores are missing due to participant too impaired, participant refused, refusal (subject or informant), physical reason or too impaired (cognitively or psychiatrically), the missing LNS total raw score will be imputed with the sum of completed item scores, and the longest LNS total raw score will be imputed with the count of longest sequence (string) numbers and letters correctly reproduced by participant.

For each of the individual component tests in the PSP cognitive composite battery, if partial item scores within a test are missing due to participant too impaired, participant refused, refusal (subject or informant), physical reason, or too impaired (cognitively or psychiatrically), the missing test score will be imputed using the sum of completed item scores.

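### As visibly written, the cognitive composite drops a subtest never started because of impairment, so that participant can score better than one who attempts it and fails

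*SAP*

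**What the plan says.** Section 5.3.1.3 of the placebo-controlled SAP builds the composite from 13 subtests in three domains. One domain has three tests ("Visual-Motor function: Figure Copy, Coding and Figure recall") and the other two have five each. For each subtest "a z-score will be calculated based on scores from baseline data of PASSPORT study". The lines that follow are redacted. The visible text then resumes: a domain score is "calculated as the sum of z-scores of the completed tests divided by the number of tests completed", and the composite is "calculated as the average of three domain z-scores". The one visible limit is "If there are any missing values for domain z-scores, then no final composite z-score will be calculated".

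Section 5.1.2 deals with scores missing because of impairment, refusal or a physical reason:

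- **Color Trails Test (not part of the composite).** Any score missing for these reasons, or because the pretest was failed, takes the worst value: "the missing values will be imputed to 240 seconds".
- **Composite subtest with some items missing.** In this case "the missing test score will be imputed using the sum of completed item scores", so items not done add nothing.
- **Composite subtest with no item done.** No rule is visible.

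**The concern.** Losing the ability to do a test is part of the decline that this battery is meant to detect. Section 5.1.2 accepts that in two of its three cases. In the third, the domain average silently runs over fewer tests, and usually the weakest one has gone. Change from baseline then compares different sets of tests, and the result can have the wrong sign for an individual.

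The planned missing-data analyses do not address this. When one subtest drops out, the composite is still calculated, so the pattern mixture model applied to this endpoint (5.2.4.5, 5.3.1.5) has nothing to impute. How a participant is scored would then depend on whether the rater recorded a test as not done or as a failed attempt.

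**Working it through.** The documents give no SD, target effect or other figure for the composite, so there is no stated number to reproduce. The check applies the visible scoring rule.

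**Inputs from 5.3.1.3.** A domain is the mean over completed tests, and the composite is the unweighted mean of three domains. Domain size k is 3 or 5, so one test carries 1/9 or 1/15 of the composite.

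**Assumed, because the documents do not give them.** Failed (floor) z of -1 to -3; mean z of the other tests in the domain of -0.5, varied to -1.5; difference between arms in the share with an undone test of 5 to 10 percentage points.

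**Gap for one participant.** Let m be the mean z of the other tests and f the z of a failed attempt.

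- Domain score if not done: m. If attempted and failed: ((k-1)m + f)/k.
- Domain gap: (m - f)/k. Composite gap: (m - f)/(3k).

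| k | m | f | Composite gap |
|---|---|---|---|
| 3 | -0.5 | -1 | 0.5/9 = 0.056 |
| 3 | -0.5 | -2 | 1.5/9 = 0.167 |
| 3 | -0.5 | -3 | 2.5/9 = 0.278 |
| 5 | -0.5 | -1 | 0.5/15 = 0.033 |
| 5 | -0.5 | -3 | 2.5/15 = 0.167 |
| 3 | -1.0 | -1 | 0 |
| 3 | -1.5 | -1 | -0.5/9 = -0.056 |

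The last two rows show that the advantage disappears when the other tests are as low as the floor, and reverses when they are lower.

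**Apparent improvement.** Take baseline visual-motor z-scores of 0, 0 and -2, with the other domains at 0. The baseline composite is (-2/3)/3 = -0.222.

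- Later the third test is not started and the others stay at 0. The composite is 0, a change of +0.222.
- Later the third test is not started and the others fall to -0.5. The composite is -0.5/3 = -0.167, a change of +0.056. Had the third test been done and stayed at -2, the domain would be (-0.5 - 0.5 - 2)/3 = -1.0 and the composite -0.333, a change of -0.111.

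**Arm level.** Bias in the treatment difference is the difference in affected share times the gap, if the gap is the same in both arms.

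- Smallest: 0.05 x 0.033 = 0.002 z. Largest: 0.10 x 0.278 = 0.028 z.
- Equal shares of 10% in both arms, with m - f of 1 to 2 in the three-test domain: each arm's mean is raised by 0.10 x 1/9 = 0.011 to 0.10 x 2/9 = 0.022 z, and the treatment difference does not change.

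**The case against.** The strongest reply is the redaction. Hidden lines stand between the z-score reference and the domain rule, and the SAP does not visibly define a completed test. A rule for undone subtests could be there. That stands, so the point concerns the visible text and the fix is conditional. Section 5.1.2, which is the place for such rules, is readable on this matter and has none.

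A reader might infer more than the documents support:

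- **That any impaired participant gains.** A test begun and not finished counts its undone items as zero, so only a test never started is affected, and then only if it would have scored below the others in its domain.
- **That the most impaired participants are removed.** If a whole domain is lost, the composite is missing at that visit, but the mixed model (5.1.4) uses the other visits under missing at random. Withdrawals for reasons possibly related to efficacy are also handled by reference-based imputation in the pattern mixture model. That model does keep missing at random for missing data not caused by withdrawal.
- **That the comparison is pulled toward no difference, or that harm is hidden.** This needs undone tests to differ between arms in frequency or in gap. The documents give no rates, and a difference could act either way.

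Two further points limit the consequence. Entry requires an MMSE of at least 20 and the ability to comply with neuropsychological evaluation for 52 weeks (protocol 6.1.2), which works against frequent non-performance. The composite can also be claimed only after the primary endpoint, MDS-UPDRS Part II and CGI-C succeed. Neither point settles how an undone subtest is scored.

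Finally, giving the lowest score to Figure Copy, Coding or Figure Recall when the reason is physical could record motor or visual loss as cognitive decline. That is a fair objection to applying the Color Trails rule unchanged, and the fix allows for it.

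**Conclusion.** The concern holds in a limited form. On the visible text, a composite subtest never started because of impairment drops out of the average, while 5.1.2 penalises the same impairment in the two neighbouring cases. The participant can then score better than one who tries and fails, and can show an apparent gain from baseline.

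For an individual the shift is not trivial: about 0.06 to 0.28 z with one undone test in the three-test domain, and 0.03 to 0.17 z in a five-test domain. At arm level it is small, roughly 0.002 to 0.03 z, and zero if undone tests are alike in both arms. These sizes rest on the assumed z-scores and rates. Without a composite SD or target effect, the documents do not show whether such a bias would change the test result. The correction is worth making because the endpoint is key secondary and the scoring gap is inexpensive to close.

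**What to change.** Unless the redacted text already does so, amend 5.1.2 and 5.3.1.3 of the placebo-controlled SAP as follows:

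1. A composite subtest with no item done because the participant is too impaired takes its lowest possible raw score before z-scoring. List that score for each of the 13 subtests. The printed ranges need checking: Letter Number Sequencing starts at 0 (5.3.2.4), but each phonemic fluency trial starts at 1 (5.3.2.3).
2. Average over completed tests only when a test is missing for another reason, and define a completed test.
3. Keep the present completed-tests rule as a sensitivity analysis.
4. Add a sensitivity analysis that also gives the lowest score to tests not done for a physical reason or refusal.
5. Tabulate wholly undone subtests by arm, visit and reason.

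The extension SAP takes its missing-item rules from the placebo-controlled SAP (its 5.2), so the change should carry over. The cost is SAP wording, one derivation rule based on reason categories that 5.1.2 already applies, and the added sensitivity runs and table. The drawback is some floor effect in the composite.
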